9.1. Ethics approval

This study will involve human subjects and as such, ethical considerations will be paramount. The study will be conducted in accordance with the principles of the Declaration of Helsinki and will comply with all relevant laws and regulations. All patients will be fully informed of the risks and benefits of participation in the study and will provide written informed consent prior to enrolment. The Chief Investigator will obtain approval from the Kaunas regional biomedical research ethics committee.

9.2. Consent

Consent to enter the study must be sought from each participant only after a full explanation has been given, an information leaflet offered and time allowed for consideration. Signed participant consent should be obtained. The right of the participant to refuse to participate without giving reasons must be respected. After the participant has entered the study the clinician remains free to give alternative treatment to that specified in the protocol at any stage if he/she feels it is in the participant's best interest, but the reasons for doing so should be recorded. In these cases the participants remain within the study for the purposes of follow-up and data analysis. All participants are free to withdraw at any time from the protocol treatment without giving reasons and without prejudicing further treatment.

9.3. Risks of procedure

The procedure carries certain risks including potential vascular injury during catheter insertion, which might lead to bleeding or hematoma. It can also induce abnormal heart rhythms, some potentially life-threatening, and in rare instances, provoke heart attacks or worsen angina. Patients are exposed to ionizing radiation due to fluoroscopy, and while the risk is minimal, it's still present. Additionally, there's a possibility of allergic reactions to the contrast dye and, as

with any invasive procedure, a risk of infection at the insertion site. Despite these risks, the procedure's benefits usually outweigh potential downsides, but patients should be well-informed and provide consent.

9.4. Confidentiality

The Chief Investigator will preserve the confidentiality of participants taking part in the study and is registered under the Data Protection Act.

9.5. Indemnity

Lithuanian University of Health Sciences holds negligent harm and non-negligent harm insurance policies which apply to this study.

9.6. Sponsor

Lithuanian University of Health Sciences will act as the main Sponsor for this study. Delegated responsibilities will be assigned to the NHS trusts taking part in this study.

9.7. Funding

This study is not funded

9.8. Audits

The study may be subject to inspection and audit by Lithuanian University of Health Sciences under their remit as sponsor and other regulatory bodies to ensure adherence to GCP.

10. Study management

The day-to-day management of the study will be co-ordinated through **Lithuanian University of Health Sciences**.

10.1. Study reporting

Upon the completion of the study and subsequent data analysis, our findings will be compiled and prepared for dissemination in May 2024. The results will be structured following the typical format of an original research article, with sections including Introduction, Methods, Results, Discussion, and Conclusion. Preliminary findings will first be presented to the investigative team.

Feedback will be incorporated, and a finalized report will be prepared for submission to a peer-reviewed medical journal. Besides, we will seek opportunities to present our findings at relevant conferences and symposia, ensuring a wider reach among the medical and research community. All data will be archived as per regulatory guidelines, ensuring transparency and facilitating future reference or studies. Any post-publication queries or feedback will be addressed promptly by the research team.

10.2. Study sites and enrollment

The COMET-19 study will be conducted at two primary sites in Lithuania:

1. Klaipeda University Hospital, Klaipeda: This facility has established itself as a reputable institution for patient care and clinical research. The infrastructure, coupled with the expertise of the clinical team, makes it a suitable site for the study's requirements.

Given its strategic location and catchment area, it is anticipated that a significant portion of the study's participants will be enrolled from this facility.

2. Hospital of Lithuanian University of Health Sciences Kaunas Clinics, Kaunas: As a part of one of Lithuania's premier health sciences universities, this hospital boasts state-of-the-art facilities and a team of experienced clinicians and researchers. Its reputation and accessibility will undoubtedly contribute to a smooth recruitment process.

Both sites will be equipped with the necessary equipment, specifically the CoroFlow system and the Pressure Wire X, to ensure uniformity in the functional assessments. Enrolment targets will be set for each site, considering their patient volume and the prevalence of eligible patients. Regular coordination and communication between the two sites will be maintained to ensure consistency in recruitment, assessment, and documentation. The chief investigator, alongside site coordinators, will continuously monitor the enrolment pace and address any discrepancies or challenges that may arise during the study's course.

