1.1. Study summary

Design

The COMET-19 study is a prospective cohort study that aims to compare the prevalence of coronary microvascular dysfunction (CMD) in patients with stable angina who have a history of severe COVID-19 infection and those with stable angina without a history of COVID-19.

Aims

The primary aim of the study is to determine whether a history of severe COVID-19 infection impacts the prevalence of CMD and its endotypes in stable angina patients.

Outcome measures

The primary outcome measure will be the prevalence of CMD in both groups, measured by both coronary flow reserve (CFR) and index of microvascular resistance (IMR) using a pressure-temperature wire.

Population

The study population for the COMET-19 trial consists of adult patients (aged 40 -80 years) with a clinical diagnosis of stable angina. They will be recruited from two university hospitals in Lithuania: Seamen's Branch, Klaipeda University Hospital, Klaipeda, and the Hospital of Lithuanian University of Health Sciences Kaunas Clinics, Kaunas.

Eligibility

Eligible patients will be those who have been diagnosed with stable angina and are scheduled to undergo angiography and possible revascularization. The study population will be divided into two groups:

Group A: Patients with stable angina and a history of severe COVID-19 infection.

Group B: Patients with stable angina without a history of COVID-19 infection. This group serves as a comparison group to assess the potential differences in CMD prevalence.

Duration

Anticipated recruitment is 6 months. Follow-up will occur 3 months after coronary angiography

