4.5. Sample size/Power calculation

Prior literature suggests that the prevalence of CMD in patient with stable angina is approximately 10% (4). There is minimal data on the prevalence of CMD in stable angina patients with a history of COVID-19 infection. Limited preliminary data from the ANGI-Covid study suggests the prevalence to be approximately 50% (5).

After adjusting each estimated prevalence 5% towards each other, the estimated prevalence of CMD in patients with stable angina was set at 15% and in patients with stable angina with a history of COVID-19 infection at 45%. For a study power of 0.9, we will require a total of 94 patients in the study, with 47 patients in each arm of the study. Given the uncertainty regarding the estimated prevalence of CMD in patients with stable angina with a history of COVID-19 infection, this study will adopt an adaptive study design. Once enrollment has been completed based on the abovementioned estimates, the necessary sample size will be re-assessed to statistical power based on the observed prevalence of CMD within in each of the present cohort. At that time, the decision will be made to continue or halt enrollment depending on whether the necessary number of enrollees for statistical significance for the primary endpoint has been reached.

13. Participant entry

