5.1. Pre-registration evaluation

Recruitment

Recruitment will be conducted in two main university hospitals in Lithuania. Physicians will be trained to identify potential candidates during their regular visits. Information brochures will be

provided in waiting rooms and clinics to raise awareness about the study. Additionally, potential participants might be contacted via phone or email, if they previously agreed to be informed about research opportunities.

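### Enrolment targets are set per site but not per group within site, and the primary test ignores site, so the Group A v Group B contrast can become partly a contrast between hospitals

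*Combined protocol and SAP*

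**What the plan says.** All references are to the combined protocol and SAP.

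- **Design (section 1.1).** "The COMET-19 study is a prospective cohort study". Group membership follows from COVID-19 history, so randomisation does not spread the groups across hospitals. On timing: "Anticipated recruitment is 6 months".
- **Sites (section 10.2).** "The COMET-19 study will be conducted at two primary sites in Lithuania". On numbers: "Enrolment targets will be set for each site, considering their patient volume and the prevalence of eligible patients". For Klaipeda, "it is anticipated that a significant portion of the study's participants will be enrolled from this facility". No figure is attached, and none is given by group.
- **Group sizes (section 4.5).** The only group-level number is the overall one: "with 47 patients in each arm of the study".
- **Standardisation (section 10.2).** Both hospitals are to have the same CoroFlow system and pressure wire, "to ensure uniformity in the functional assessments", and the sites are to coordinate on recruitment and assessment. Nothing is said about operators.
- **Analysis (section 8).** CMD is compared between groups with a chi-square or Fisher's exact test. No site term, stratification, matching or regression is named. Centre is on the baseline list in section 4.2, but no stated analysis uses it.

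**The concern.** Section 4.5 fixes the group totals. Section 10.2 says that site totals will be fixed. Nothing joins the two, so the plan allows one hospital to supply more of Group A and the other more of Group B. The primary test pools the hospitals and would then attribute to COVID-19 any difference between them in case mix or in how CFR and IMR are obtained.

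This matters because the endpoint is a dichotomy at fixed cut-offs (section 6.1: IMR above 25 or CFR below 2.0), so a shift in measurement at one site can reclassify patients near a threshold. Section 3.2 also intends to read the result as evidence on whether the virus has a direct part in causing CMD. A distortion could go either way: it could produce a difference, or hide a real one if the hospital supplying more of Group A has the lower measured prevalence.

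The groups could likewise be enrolled at different times within the recruitment period. That is only a possibility, and the documents give nothing with which to size it.

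**Working it through.** **1. The plan's own figure.** Inputs from section 4.5: 15% v 45%, power 0.9. From section 8: significance level 0.05 (two-sided assumed, since sidedness is not stated). With pooled variance and no continuity correction:

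n = [1.96·√(2·0.30·0.70) + 1.2816·√(0.15·0.85 + 0.45·0.55)]² / 0.30² = (1.270 + 0.785)² / 0.09 = 46.9, so 47 per group and 94 in total.

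The stated sample size reproduces. The point does not touch that arithmetic.

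**2. Size of a site-induced difference.** With no COVID-19 effect,

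spurious A − B difference = (share of A at site 1 − share of B at site 1) × (CMD prevalence at site 1 − CMD prevalence at site 2).

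It is zero if either bracket is zero. The documents give neither the split nor the site prevalences, so both are assumptions, shown over a range. Example: 35 of 47 v 12 of 47, and 20% v 10%: (23/47) × 0.10 = 4.9 points.

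**3. False-positive rate of the planned test.** This is an exact enumeration of the two-sided uncorrected chi-square test at 47 v 47, each group's CMD count being the sum of two site-specific binomials. Site 2 prevalence is 10% throughout.

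| Group A v Group B at site 1 | Site 1 prevalence | Spurious difference | False positives |
|---|---|---|---|
| 24 v 23 | 20% / 25% / 30% | 0.2 / 0.3 / 0.4 points | 5.3% / 4.9% / 4.5% |
| 28 v 19 | 20% / 25% / 30% | 1.9 / 2.9 / 3.8 points | 6.1% / 6.4% / 6.8% |
| 35 v 12 | 20% / 25% / 30% | 4.9 / 7.3 / 9.8 points | 10.6% / 15.5% / 21.5% |

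**4. Adjusting for site in the analysis only.** Simulating a two-sided Mantel-Haenszel test stratified by site, the 35 v 12 split gives about 5% false positives in all three prevalence cases. Power for 15% v 45% is about 81%, against about 91% when the groups are balanced within site.

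The loss can be seen by hand. The information in the stratified comparison is the sum over sites of nA·nB/(nA + nB). Balanced, this is 47/2 = 23.5. At 35 v 12 it is 2 × (35·12/47) = 17.9. The ratio is 0.76, equivalent to 0.76 × 47 ≈ 36 per group.

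On the same approximation, a site-stratified analysis with 47 per group has about 89% power at a 60/40 v 40/60 mix, 84% at 70/30 v 30/70, 73% at 80/20 v 20/80 and 48% at 90/10 v 10/90. If the groups were completely separated by hospital, no site-stratified comparison would be possible.

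**5. Balancing at enrolment.** With the same site mix in both groups, the first bracket in step 2 is zero, so site differences in prevalence cause no spurious difference, and 47 per group keeps its planned power.

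**The case against.** The strongest reply is that the documents show neither condition for bias. Setting targets per site does not itself create imbalance. Nothing says that the targets will ignore group, that the A:B ratio will differ between hospitals, or that CMD differs between them. Section 10.2 commits both sites to the same equipment and to coordinated recruitment and assessment, and section 4.2 gives one measurement procedure for everyone. The larger figures need a strongly reversed split and a two- to threefold site difference in CMD together; at 28 v 19 the test stays near its nominal level. All of this stands, and it is why the point is conditional.

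Three stronger readings are tempting and are not supported:

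- *That the contrast will be a site contrast.* The text permits this but does not imply it.
- *That adjusting for centre later is of little use.* Centre is recorded, and step 4 shows that stratification restores the error rate. What it costs is power, moderately at 35 v 12 and heavily only near complete separation.
- *That the recruitment routes in section 5.1 separate the groups.* That section says that "potential participants might be contacted via phone or email, if they previously agreed to be informed about research opportunities", but the routes are open to both groups alike, and section 1.1 requires every eligible patient to be scheduled for angiography.

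The reply does not remove the gap itself. Common equipment does not equalise case mix or set an A:B ratio, and the stated primary test would neither reveal nor correct an imbalance if one arose.

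**Conclusion.** The point holds in conditional form. The plan has no group target within site and no site term in the primary comparison, so the group contrast can become partly a site contrast if both the A:B ratio and measured CMD differ between the hospitals. Under the assumed site prevalences of 20–30% v 10%, the excess is small for a mild imbalance (6.1–6.8% false positives at 28 v 19) and material for a strong one (10.6–21.5% at 35 v 12). Stratifying the analysis alone corrects the error rate but leaves about 81% power in the strong case.

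These sizes rest on splits and prevalences that the documents do not give; they show what the plan allows, not what will happen. A possible difference in enrolment time between the groups is unquantified and adds nothing to them. This is an inexpensive improvement worth making, not an error in the sample size and not evidence that the comparison is already biased.

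**What to change.** - **Section 10.2.** Set equal Group A and Group B targets within each hospital, with concurrent enrolment: for each Group A patient, enrol the next eligible consecutive Group B patient on the same hospital's angiography list. The hospitals need not be of equal size; only the 1:1 ratio within each matters. Concurrent enrolment also covers the possibility of a calendar-time difference.
- **Section 8.** Make the primary comparison of CMD prevalence a site-stratified Mantel-Haenszel test, using the centre variable already collected, and report the group-by-site table.

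The cost is protocol wording and some enrolment bookkeeping. Total enrolment stays at 94. The downside is that Group B recruitment is paced by Group A, so Group B may finish later than it otherwise would.

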10.3. Documentation

All trial documentation will be systematically collected and managed using Google Sheets, which offers robust functionality for multi-center international studies such as ours. The use of Google Sheets facilitates real-time, secure data entry and retrieval across study sites.

10.3.1 Data Handling Procedures

- Google Sheets Setup: A master file with individual tabs for each site will be used to record clinical and physiological data.
- Data Security: Access is restricted to authorized personnel, ensuring confidentiality and integrity in line with GCP guidelines.
- Data Review: Routine checks will be performed to verify data accuracy, with corrections logged for audit purposes.
- Backups: Data will be regularly exported and backed up onto DVDs and a central server to prevent data loss and ensure recovery if needed.

13.1 Seattle Angina Questionnaire

The Seattle Angina Questionnaire-7

1. The following is a list of activities that people often do during the week. Although for some people with several medical problems it is difficult to determine what it is that limits them, please go over the activities listed below and indicate how much limitation you have had due to **chest pain, chest tightness or angina over the past 4 weeks**.

Place an X in one box on each line.

Activity	Extremely limited	Quite a bit limited	Moderately Limited	Slightly limited	Not at all limited	Limited for other reasons or did not do the activity
a. Walking indoors on level ground						
b. Gardening, vacuuming or carrying groceries						
c. Lifting or moving heavy objects (e.g. furniture, children)						

2. Over the past 4 weeks, on average, how many times have you had **chest pain, chest tightness or angina**?

I have had **chest pain, chest tightness or angina**...

4 or more times per day	1-3 times per day	3 or more times per week but not every day	1-2 times per week	Less than once a week	None over the past 4 weeks
					

3. Over the past 4 weeks, on average, how many times have you had to take nitroglycerin (nitroglycerin tablets or spray) for your **chest pain, chest tightness or angina**?

I have taken nitroglycerin...

4 or more times per day	1-3 times per day	3 or more times per week but not every day	1-2 times per week	Less than once a week	None over the past 4 weeks
					

4. Over the past 4 weeks, how much has your **chest pain, chest tightness or angina** limited your enjoyment of life?

It has extremely limited my enjoyment of life	It has limited my enjoyment of life quite a bit	It has moderately limited my enjoyment of life	It has slightly limited my enjoyment of life	It has not limited my enjoyment of life at all
				

5. If you had to spend the rest of your life with your **chest pain, chest tightness or angina** the way it is right now, how would you feel about this?

Not satisfied at all	Mostly dissatisfied	Somewhat satisfied	Mostly satisfied	Completely satisfied

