3.1 Primary, Secondary and Tertiary Objectives

1. Primary objectives:

To determine if there is a significant difference in the prevalence of coronary microvascular dysfunction (CMD) between patients with stable angina who have had a severe COVID-19 infection (Group A) and those stable angina without a history of COVID-19 (Group B). This will be measured using both coronary flow reserve (CFR) and index of microvascular resistance (IMR) through the pressure-temperature wire.

2. Secondary Objectives:

- I. To assess the severity of CMD, as indicated by the CFR and IMR values, in both groups. This will allow for a deeper understanding of the extent of CMD in each group.
- II. To evaluate any potential correlation between the duration of oxygen supplementation (in days) in the COVID-19 group and the incidence and severity of CMD. This could provide insight into whether the length of severe illness contributes to the risk or extent of CMD.
- III. To investigate which CMD endotype (structural or functional) predominates in both groups.

3. Tertiary Objectives:

- I. To investigate the patient-reported outcomes in both groups, especially in relation to symptoms of angina, quality of life, and functional status. This would give insight into how CMD affects patients' day-to-day lives and well-being.

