3.3 Study hypotheses

 Primary Hypothesis:

- i. Patients with a history of severe COVID-19 infection (those who required oxygen supplementation) (Group A) will have a higher prevalence of CMD (IMR > 25 or CFR < 2.0) than patients without a history of COVID-19 infection (Group B).

 Secondary Hypotheses:

[figure not shown]
- i. Patients in Group A will have more severe CMD than patients in Group B.
- ii. The severity of CMD will correlate with the duration of oxygen supplementation.

 Tertiary Hypothesis:

- i. Group A will have worse patient-reported health outcomes than patients in Group B.

13. Study design

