4.1 Study overview diagram

4.2 Study protocol:

Following enrollment in the study patients should undergo the following:

Baseline assessment:

- A. Demographics:
 - Age
 - Gender
 - Center
 - Rural vs Urban
- B. Medical History:
 - History of cardiovascular diseases (specifically any known coronary artery disease)
 - History of diabetes, hypertension, or other comorbid conditions
 - Medications currently being taken
 - Past surgeries or medical interventions
- C. COVID-19 Specific History (for Group A):
 - - Date of COVID-19 diagnosis
 - - Duration of hospitalization
 - - Length of time on oxygen supplementation
 - - Any other COVID-19 related complications experienced
- D. Clinical Assessment:
 - Vital signs (Blood Pressure, Heart Rate, Respiratory Rate, Temperature, Oxygen Saturation)
 - - Body Mass Index (BMI)
 - -Physical examination focusing on the cardiovascular system
- E. Symptom Assessment:
 - Onset, frequency, duration, and severity of angina symptoms
 - Presence of any other cardiovascular symptoms (e.g., shortness of breath, palpitations)
 - New York Heart Association classification
- F. Diagnostic Tests:
 - Electrocardiogram
 - Echocardiogram or other imaging if available and relevant
 - Blood tests (cardiac markers, lipid profile, Inflammatory markers, blood glucose, blood counts and renal function panel)
- G. Patient-Reported Outcomes:
 - Quality of Life assessment, (Seattle angina score)

H. Risk Factors:

-  - Smoking history
-  - Alcohol consumption
-  - Physical activity levels
-  - Family history of cardiovascular diseases

I. Review of Previous Treatments (if any):

-  - Medications previously prescribed for angina (Trimetazidine, Ranolazine, cardiovascular related drugs)

Functional assessment

Functional assessment will be performed just after undergoing the diagnostic coronary angiography

Invasive functional assessment

- Upon intubation of the guiding catheter, 300 mcg of intra-coronary glyceryl-trinitrate will be administered to control coronary vasomotor tone.
- Coronary flow reserve (CFR), fractional flow reserve (FFR), and index of microvascular resistance (IMR) will be assessed using the CoroFlow system (Coroventis Research AB, Uppsala, Sweden).

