1. Data Management: All data collected will be entered into a secure, electronic database with backup systems in place. Double-entry methods and routine cross-checks will be implemented to minimize data-entry errors.
2. Descriptive Statistics: Basic statistics like mean, median, standard deviation, and interquartile ranges will be utilized to describe continuous variables. For categorical variables, frequencies and percentages will be used.
3. Comparative Analysis: To compare the incidence of CMD between Group A (COVID-19 with oxygen supplementation) and Group B (no history of COVID-19), a Chi-square test or Fisher's exact test will be employed for categorical variables, and the t-test or Mann-Whitney U test will be used for continuous variables, depending on the data distribution.
4. Correlation Analysis: Pearson's or Spearman's rank correlation will be used to assess the relationship between the duration of oxygen supplementation and the severity of CMD.
5. Significance Level : A p-value of less than 0.05 will be considered statistically significant for all tests.
6. Multiple Testing: Adjustments for multiple comparisons, if applicable, will be done using methods like the Bonferroni correction to prevent type I errors.
7. Missing Data: Any missing data will be addressed using suitable imputation methods. The extent and pattern of missing data will be analyzed, and if it's determined to be missing at random, multiple imputation methods may be used.
8. Subgroup Analysis: If sample size permits, further subgroup analyses might be performed to identify any trends or patterns within specific subsets of the population, such as based on age, gender, or other relevant factors.

9. Graphical Representation: Key results will be depicted using appropriate charts and graphs to aid in the visualization and interpretation of findings.

10. Software: All statistical analyses will be performed using a validated statistical software package like SPSS, R, or Stata.

11. Reporting: Results will be reported in accordance with relevant guidelines for observational studies, ensuring clarity, transparency, and reproducibility.

9. Regulatory issues

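### The only patient-reported instrument, the SAQ-7, is angina-specific, so the Group A versus Group B comparison cannot support the wider claims about functional status and health outcomes in 3.1 and 3.3

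*Combined protocol and SAP*

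**What the plan says.** - **Objective (3.1, Tertiary Objective I).** Patient-reported outcomes are to be studied in both groups, "especially in relation to symptoms of angina, quality of life, and functional status".
- **Hypothesis (3.3, Tertiary Hypothesis).** "Group A will have worse patient-reported health outcomes than patients in Group B". This is not confined to angina.
- **Instrument (4.2, G).** The patient-reported entry is "Quality of Life assessment, (Seattle angina score" and nothing else. Section 4.2 has it given once, before angiography. Section 4.3 lists its score among the secondary outcomes. The appended form (13.1) is "The Seattle Angina Questionnaire-7".
- **Item 1 (13.1).** Three activities are rated on five graded levels of limitation caused by chest pain or angina. The preamble concedes the attribution problem: "Although for some people with several medical problems it is difficult to determine what it is that limits them". A sixth box, outside the graded levels, reads "Limited for other reasons or did not do the activity". Items 2 to 5 also concern only chest pain or angina and have no such box.
- **Scoring.** No rule is given for the SAQ score or for the sixth box.
- **Missing data (section 8, item 7).** "Any missing data will be addressed using suitable imputation methods". Nothing in it is specific to the questionnaire.
- **Other functional data (4.2, E).** "New York Heart Association classification" and the presence of other symptoms such as breathlessness are recorded at baseline. Neither is an outcome in 4.3 or named in section 8.

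**The concern.** The stated claim is wider than the measurement. Group A is defined by COVID-19 with hypoxaemia that needed oxygen (5.2), and section 2.1 describes symptoms that persist after recovery. Exclusion 11 removes only patients on long-term oxygen before COVID-19, so patients with residual respiratory limitation can enter Group A. Their non-angina limitation has no graded place on the form. It is plausible, though not documented, that they will tick the sixth box more often than Group B.

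A null SAQ difference could then be reported as no worse functional status after severe COVID-19, when the instrument was never in a position to show it. Because the handling of the sixth box is left open, the item 1 comparison also depends on a scoring choice that could be made after the data are seen.

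**Working it through.** **The plan's own figure.** There is none for the SAQ comparison. The sample size in 4.5 sets the precision and reproduces. With 15% versus 45%, two-sided 0.05, power 0.9 and pooled variance:

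n = [1.960·√(2·0.30·0.70) + 1.282·√(0.15·0.85 + 0.45·0.55)]² / 0.30² = (1.270 + 0.785)² / 0.09 = 46.9, so 47 per arm and 94 in total.

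**Assumptions for the rest (none is in the documents).** Item 1 levels are coded 0, 25, 50, 75 and 100, with higher meaning less limited. Positive differences favour Group A.

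**1. Masking.** Let angina limitation be equal in both groups, and let 40% of Group A lose 25 points of overall function for non-angina reasons.
- True overall difference: −0.40 × 25 = −10 points (−9.7 by simulation, because the scale stops at 0).
- Item 1 difference when box use is unrelated to angina limitation: about 0, whether 25%, 50% or 100% of those affected tick the box.
- With average losses of 5 and 15 points in place of 10, the simulated true differences are −4.9 and −14.0. The observed difference is again about 0.

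**2. Unscored answers, harder activities affected.** Let the means for walking, gardening and lifting be 80, 60 and 40 in both groups (overall mean 60). Box use is 10% in Group B and 20%, 30%, 40% or 50% in Group A, and the answered items are averaged.
- Lifting lost: the patient's mean becomes (80 + 60)/2 = 70, a gain of 10. The shift is 10 × (use in A − 0.10) = +1, +2, +3, +4.
- Gardening and lifting lost: the mean becomes 80, a gain of 20. The shift is +2, +4, +6, +8.

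Simulation with correlated items gives about +0.9 to +3.8 and +1.8 to +7.5.

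**3. The same eight scenarios with imputation.** Predicting the unanswered items from the answered ones, with box use unrelated to angina limitation, brings every difference to within about 0.1 of zero.

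**4. Unscored answers, more limited patients affected.** Consider a single activity.
- Group B shares 0.05, 0.15, 0.30, 0.30, 0.20 give a mean of 61.25.
- Group A shares 0.08, 0.20, 0.32, 0.25, 0.15 give a mean of 54.75, a true difference of −6.5.
- If a fraction f of Group A's two worst levels ticks the box and nobody in Group B does, the observed Group A mean is (54.75 − 5f)/(1 − 0.28f).
- The difference is −3.7 at f = 0.25, −0.5 at f = 0.50 and +3.3 at f = 0.75.
- It is zero when 12.15f = 6.5, so f = 0.53, with 0.28 × 0.53 = 15% of Group A in the box.

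**5. Against sampling error.** With an assumed SD of 18 and 47 per arm, the standard error is 18·√(2/47) = 3.7 points and the 95% half-width is 1.96 × 3.7 = 7.3. Of the eight shifts in step 2, only the largest exceeds that half-width.

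**The case against.** **The angina-specific target is defensible.** Objective I also says that the aim is to see how CMD affects daily life, and both groups enter with CCS grade II or III angina (6.1). Breathlessness after COVID-19 pneumonia is not an effect of CMD, so leaving it out suits that aim. This stands. It is a reason to narrow the claim to angina-related health status, but it does not rescue the wider words in 3.1 and 3.3.

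**A reader might infer that functional status is not measured at all.** The documents do not support that. Item 1 measures angina-related limitation, and NYHA class is recorded at baseline. What is missing is a patient-reported measure of limitation from other causes.

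**A reader might infer that the group comparison will reverse.** One could set the +1 to +8 of step 2 beside a coding in which every box tick counts as the worst level. That coding gives 0.1 to 0.4 × −13.3 = −1.3 to −5.3 for lifting, or 0.1 to 0.4 × −33.3 = −3.3 to −13.3 for both activities. But these are two different quantities. The box also covers people who simply had no occasion for the activity, so scoring it as the worst level is an extreme. Averaging the answered items is a rule that the documents do not state. The one general rule they do state, imputation, gives about zero when box use is unrelated to angina limitation.

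**The size is limited.** Box-use rates are assumed, the arithmetic concerns item 1 only, and a score that includes items 2 to 5 would dilute any shift.

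**Conclusion.** The concern holds as a mismatch between claim and instrument. This follows from the wording of the form and needs no assumption. Non-angina limitation in Group A is not captured, so a null SAQ difference cannot be reported as no worse functional status or no worse health outcomes.

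The main effect is masking, and its size is whatever non-angina deficit exists. A shift in favour of Group A is conditional. It needs more box use in Group A, concentrated on the harder activities or among the more limited patients, and those answers left unscored. Under the assumed rates it is about 1 to 8 points on item 1, mostly within the sampling error of 47 per arm.

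Imputation does not cure the masking. It replaces an informative answer with a predicted angina limitation. The primary endpoint and the sample size of 94 are unaffected. The point should be settled before analysis.

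**What to change.** 1. In 3.1, 3.3 and section 8, limit the SAQ-7 conclusion to angina-related health status.
2. In section 8, state that the sixth box is an observed answer and not missing data for item 7, and tabulate its use per activity by group.
3. Report the activity items separately from the angina-frequency and quality-of-life items, which have no such box.
4. Compare baseline NYHA class between groups as a supportive, clinician-graded measure of functional status. Section 8, item 3 assigns the Mann-Whitney test to continuous variables, so add one sentence naming a rank test for this ordinal variable. State that it does not test the patient-reported hypothesis.

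The cost is a few sentences and one table, with no new data, visits or patients. The downsides are one more secondary comparison and a narrower patient-reported claim.
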